4.4.2. Secondary Outcomes

There will be several outcomes and subgroup analyses, including outcomes that are individual components of the broad domains already described. We consider the general question of power with a cohort of 750 as well as smaller sample sizes, by examining the relevant parameters for sample size/power assessment for a hypothesis test of a correlation between a continuous prognostic biomarker and a dichotomous or continuous one year outcome of interest using a logistic or linear regression.

For scenarios where the outcome is determined to be binary (e.g. respiratory re-hospitalization or not), we will use logistic regression to test the correlation between a biomarker and the binary outcome. If we consider a range of the outcome event rates from 30% to 50%^{1, 32, 102} and examine the same missing rates as above, we will have the same power estimate as shown in Figure 4.4.1. Please note that respiratory re-hospitalization takes discrete non-negative ordinal values and will be analyzed using the proportional-odds (or ordinal logistic) regression models to test the correlation between a biomarker and the outcome. Such models allow unequal spaced differences among ordinal scales and yet estimate the common effect of predictors on the increasing scale of the outcome. Our power estimate based on the dichotomized variable is conservative and our planned proportional odds models generally have higher power than the logistic regression for a dichotomized outcome.¹⁰³ For other secondary outcomes that might be described as approximately continuous, we can assess the value of a biomarker as the

proportion of the outcome variance explained by the biomarker (R²). One outcome that will be considered is a one year physical exam score.

Figure 4.4.2 shows the power to detect a significant association between a biomarker and a continuous outcome. For example, for the sample size of 750 and R² of 0.5% to 2% (equivalent effect sizes of 0.071 SD to 0.143 SD, which are generally considered as small effects) the power was estimated assuming conservative missing rates of 5% and 10% (as in Section 4.4.1 above) using $\alpha = 0.05$.^{104, 105} Clearly for a continuous outcome, the PROP cohort will provide sufficient power to detect significance for even a small effect size.

Figure 4.4.2: Power of detecting a significant association between a biomarker and a continuous outcome for various effect size at a significance level of α =0.05.

Since the analysis will be adjusted for covariates including gender, birth weight, and gestational age at birth, the sensitivity of the analysis may be affected by the actual correlation between the biomarker and the covariate and the effect of the covariate. If multiple independent biomarkers can jointly explain the outcome, we are likely to have higher power to detect at least one of these biomarkers.

We may investigate the biomarker-outcome association analysis in a certain gestational age group. In the power assessment to follow, since the distribution of the numbers of infants born in 23-24, 25, 26, 27, and 28 weeks is close to uniform from sites' preliminary data, we assume there are 150 infants in each group, for which the power for detecting a significant association between biomarker and continuous outcome at $\alpha = 0.05$ is shown in Figure 4.4.3. Also in the same figure, we labeled the x-axis with the corresponding odds ratios assuming the power to detect the association between a biomarker and dichotomized outcome with an event rate of 40%. Given the subgroup sample size of 150, we will have 80% power to detect a significant association for an effect size of at least 0.24 (generally considered a small effect size) for a continuous outcome or an odds ratio of 1.64 or larger (a moderate OR) for a dichotomized outcome. Note that the minimum detectable effect size (Figure 4.4.3) required for subgroup analysis is more than twice that required using the full cohort (Figure 4.4.1, 4.4.2).

Figure 4.4.3: Power of detecting a significant association between a biomarker and the dichotomized/continuous outcome for various odds ratio/effect size (top/bottom x labels) in a subgroup at a significance level of α =0.05 assuming a missing rate of 10%.

4.5. Descriptive Analysis

Before proceeding with the analysis of the PROP primary research questions, data will be fully described, including aspects of data quality. For both predictor variables and outcomes, a summary of each variable, or group of variables, will be produced. Graphical methods including histograms, scatter plots, and box plots, will be used at this stage in order to understand aspects of data quality and examine assumptions underlying statistical models. Means, standard deviations, medians, and ranges will be computed for measured continuous variables; marginal distributions will be used for categorical factors. The amount and patterns of missing data, if any, will also be characterized. Before specific research questions are addressed, several types of data manipulation may be considered. Transformations will be used if needed to produce variables that conform to the distributional assumptions underlying the analytic techniques that will be employed. For instance, some variables may be transformed to log scales, as needed to reduce any marked positive skew. Exploratory analyses and careful collaboration with investigators will be used to guide in the selection and creation of summary variables.

4.6. General Statistical Analytic Approaches

Most standard hypothesis tests will be specified as using a two-sided significance level (Type I error) of α = 0.05, although actual p-values will be reported whenever possible. For measured continuous variables, two-group comparisons will generally employ Wilcoxon rank-sum tests to protect against violations of normality assumptions. The Wilcoxon test affords little loss of power, as it is more than 95% efficient with respect to the two-sample t-test when normality holds. Similarly, Wilcoxon signed-rank tests will be used for paired data and Kruskal-Wallis tests will be used for k-group comparisons. In some instances, t-tests and analysis of variance (ANOVA) methods may be used to facilitate group comparisons when the appropriate assumptions are met. Categorical variables,

including dichotomous factors, will be summarized by proportions and compared among groups using standard chi-square tests of association and generalized Mantel-Haenszel (MH) methods, as described in Landis et al¹⁰⁶ to accommodate both nominal and ordinal measurement scales. These MH methods are useful for adjusting primary associations for potential confounders. Whenever possible, exact p-values from Exact Conditional Tests, such as Fisher's exact test and its multidegree of freedom extensions, will be produced for these tests.

4.6.1. Univariate Models

Candidate biomarkers for inclusion in multivariate modeling will be assessed using marginal models or simple two way analyses, depending on the structure of the biomarker, to ascertain predictive value, if any. At this stage of model selection, factors will be moved forward for further evaluation if either their predictive value produces a p value of \leq 20% or they are biomarkers supported in the literature.

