2.3. Study Population

The risk of short and long-term respiratory morbidity in preterm infants is inversely related to gestational age at birth. This is why the PROP investigators will study the most immature infants <29 weeks of gestation in this multi-center protocol. Importantly, infants who die early during their NICU stay will not contribute any data towards the major goal of this project, which is the prediction of post-prematurity respiratory disease up to one year of age. It is readily seen by comparing Tables 2.3.1 and 2.3.2 that one approach might have been to wait until the infants have survived at least 7 days before enrolling them in PROP. This would clearly lessen the loss of study participants due to early mortality from the 1 year cohort of survivors. However, several sites have parallel evaluations of the PROP study participants for their single center protocols that require the collection of biospecimens shortly after birth.

Gestational Age	Percent of total admissions <28 weeks excluding nonviable infants	Mortality to 1 year
23	8%	44%
24	20%	28%
25	22%	15%
26	26%	19%
27	24%	7%

Table 2.3.1 Gestational age distribution of recent admissions at Vanderbilt University, with mortality through the 1st year of life, among infants who survived at least 2 days

Table 2.3.2 Gestational age distribution of recent admissions at Vanderbilt University, with mortality through the 1st year of life, among infants who survived at least 7 days

Gestational Age	Percent of total admissions <28 weeks excluding nonviable infants	Mortality to 1 year
23	5%	17%
24	19%	18%
25	22%	16%
26	28%	13%
27	26%	3%

An alternative approach is to have few restrictions on the probability of the initial survival but to "replace" children who die with new recruits. Therefore, PROP infants who do not survive to 36 weeks PMA will be "replaced" by new participants to achieve the desired target sample size of 750 infants who are likely to survive to one year. The early deaths will be used in the assessment of total mortality as a secondary outcome.

Moreover, early mortality will be strongly correlated with the degree of immaturity (Tables 2.3.1 and 2.3.2). To optimize the numbers of infants who will be available for follow up through the first year of life at each week of gestational age between 23 and 28 weeks, we propose to enroll the PROP study participants in the following 5 strata:

- i. 23 0/7 to 24 6/7 weeks GA
- ii. 25 0/7 to 25 6/7 weeks GA

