- iii. 26 0/7 to 26 6/7 weeks GA
- iv. 27 0/7 to 27 6/7 weeks GA
- v. 28 0/7 to 28 6/7 weeks GA

Without this stratification, the final cohort of survivors at 1 year would contain only a small minority of the most immature infants who are born at the margin of viability. One of the greatest benefits of identifying additional biomarkers for respiratory morbidity in the first year of life would be the stratification by risk within gestational age groups with the potential to identify phenotypic subgroups, patient-specific mechanisms and therapeutic targets. It is therefore important to enroll sufficient participants to allow data analysis within gestational age subgroups.

The DCC will monitor the number of infants who survive to 36 weeks PMA in each of the 5 strata. Enrollment into a particular stratum will end as soon as 150 survivors to 36 weeks PMA have been documented.

The most immature infants born at 23 and 24 weeks gestation have been combined into one stratum because the investigators in the 6 clinical sites are concerned that they will not be able to enroll 300 survivors to 36 weeks PMA who are born at these very low gestational ages. However, in the event that enrollment and/or survival at these low gestational ages is higher than anticipated, we will not limit the number of infants in stratum 1 to a total of 150 infants.

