4.6.2. Multivariable Models

Multivariate models will be used to both simultaneously assess the contributions of the many biomarker predictors as well as to control for factors such as gender, race, products of multiple gestation, birth weight, gestational age at birth, site differences and between hospital variation, in the evaluation of potentially complex associations. Models specified in the protocol will include linear regression for continuous outcomes and logistic regression for binary or ordinal responses. We will provide in the analyses, in addition to tests of significance, confidence intervals for parameters of risk factors and biomarkers, and various approaches to assess the robustness of the estimates to nuisance factors. Particular attention will be paid to unusual observations (outliers) that may have undue influence on the analytical results. Standard regression diagnostics, including residual plots, and influence statistics will be used to identify such observations and examine their effect on analyses.

4.6.3. **Repeated Measurements**

For repeated measures, we will use generalized linear mixed models (GLMM¹⁰⁷) to account for dependence of the measures within subjects. We will first check for patterns in the residuals from the model without any random effect to determine plausible covariance structures that may account for the temporal correlation within subject¹⁰⁸ and then select the best one using routine likelihood-based criteria: maximized likelihood, largest Akaike information criteria (AIC¹⁰⁹), Schwarz information criterion (SBC¹¹⁰). We will use maximum likelihood method (ML) and residual maximum likelihood method (REML) for parameter estimates and significance testing.

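### The univariate screen in 4.6.1 omits gestational age, so a novel marker whose link to gestational age opposes its own effect can be dropped before any adjusted model

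*Protocol*

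**What the plan says.** Section 4.6.1, headed as univariate models, sets the gate: "Candidate biomarkers for inclusion in multivariate modeling will be assessed using marginal models or simple two way analyses". The rule is that "factors will be moved forward for further evaluation if either their predictive value produces a p value of" 20% or less, "or they are biomarkers supported in the literature". No covariate is named at this step.

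Adjustment comes afterwards. Section 4.6.2 uses the multivariable models to "control for factors such as gender, race, products of multiple gestation, birth weight, gestational age at birth" and other factors. Section 4.4.2 takes the same view: "Since the analysis will be adjusted for covariates including gender, birth weight, and gestational age at birth".

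Section 2.3 says "The risk of short and long-term respiratory morbidity in preterm infants is inversely related to gestational age at birth". It enrols in five gestational-age strata and names "stratification by risk within gestational age groups" among the greatest benefits of finding new markers. Aim 4 in section 2.2 concerns novel, putative biomarkers.

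**The concern.** The gate and the models behind it ask different questions. The gate asks whether a marker is associated with post-prematurity respiratory disease (PRD) across all gestational ages together. The later models, and the within-group aim, ask whether it is associated at a given gestational age. When the marker and PRD are both related to gestational age, the two answers can differ.

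The harmful case is a marker that raises risk at a given gestational age but also rises with maturity. Maturity lowers risk, so the two effects partly cancel in the unadjusted analysis and the marker may miss even a lenient threshold. No adjusted model then tests it, and the adjusted results show no sign that it was lost. The direction of confounding is not known in advance for a novel marker.

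**Working it through.** **Inputs from the protocol (4.4.1, 4.6.1).** N = 750 less 10% missing gives n = 675. The PRD rate is 40%, the OR is 1.25 per SD, two-sided alpha is 0.05, and the screening threshold is p ≤ 0.20.

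**Assumed inputs.** The protocol gives neither r, the marker's correlation with gestational age (GA), nor the OR per +1 SD of GA. Both are varied below. The five strata are taken as equal, 135 infants each.

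**Step 1: the plan's own figure.** Power = Φ(√(n·p(1−p))·ln OR − 1.96). Here √(675 × 0.40 × 0.60) = 12.73 and ln 1.25 = 0.223, so the signal is 2.84 and power = Φ(0.88) = 81%. The stated power above 80% reproduces.

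**Step 2: the same marker at the screen, uncorrelated with GA.** The two-sided 0.20 threshold is z = 1.282, so the pass rate is Φ(2.84 − 1.28) = 94%. Without confounding, the gate is generous.

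**Step 3: the effect of omitting GA.** To a first approximation, the unadjusted log OR is ln(OR marker) + r·ln(OR GA). The pass rate is Φ(s − 1.282) + Φ(−s − 1.282), with s = 12.73 × that slope.

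- Weak opposing confounding (r = +0.2, GA OR 0.8): slope 0.223 − 0.2 × 0.223 = 0.179; s = 2.27; pass rate 84%.
- Stronger opposing confounding (r = +0.3, GA OR 0.6): slope 0.223 − 0.3 × 0.511 = 0.070, an unadjusted OR of about 1.07; s = 0.89; pass rate 36%.

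With GA in the screen the signal is 2.84 × √(1 − r²). That is 2.78 and 2.71 in these two cases, with pass rates of 93% and 92%.

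**Step 4: simulation.** Simulated logistic data for 675 infants, adjusted OR 1.25, give:

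| r | GA OR per SD | Pass, GA omitted | Pass, GA in screen |
|---|---|---|---|
| +0.2 | 0.8 | about 83% | 93–94% |
| +0.3 | 0.7 | about 57% | 91–92% |
| +0.3 | 0.6 | about 33% | 91–92% |
| −0.3 | 0.67 | over 99% | about 90% |

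Over a wider grid (r from +0.2 to +0.5, GA OR 0.8, 0.67 and 0.5), pass rates run from about 19% to 84% with GA omitted and from 86% to 94% with GA included. At the worst point of that grid (r = +0.3, GA OR 0.5), 62% of simulated cohorts had a GA-adjusted p below 0.05 but failed the unadjusted gate.

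**Step 5: markers that only stand in for GA.** With an adjusted OR of 1.00 and r = −0.3, 34%, 58% and 89% pass the unadjusted screen at GA OR 0.8, 0.67 and 0.5. About 20%, the nominal rate, pass with GA included. Once GA is in the later model, about 5% reach p < 0.05, which is also nominal.

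**The case against.** Several counter-arguments stand and limit the point.

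- **The loss is conditional.** It needs confounding that opposes the marker's effect. The protocol identifies no such marker, and under weak confounding most still pass.
- **The literature route is a real bypass.** Several physiological predictors have cited support in the protocol, for example the tidal-flow timing ratio and bronchodilator response (3.2.2) and sleep desaturation (3.2.4). Exposure is mainly among novel markers.
- **There is a second route to the within-group aim.** Sections 2.3 and 4.4.2 foresee analyses inside single gestational-age groups, and nothing sends these through the gate. They are optional, however, and have 80% power only from an OR of 1.64, so they soften the problem without removing it.
- **The study generates hypotheses (4.1, 4.6.4).** This bears on severity. It does not justify the gate, because 4.6.4 avoids strict multiplicity control precisely so as not to miss important markers.

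A reader might also infer three stronger conclusions that the protocol does not support:

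- **Gestational-age proxies will be reported as findings.** They pass the screen too often, but 4.6.2 and 4.4.2 then adjust for gestational age. What remains is a longer candidate list.
- **The power statement in 4.4.1 is wrong.** It states its assumption of no correlation between marker and covariates and reproduces under it. Section 4.4.2 warns that such correlation affects sensitivity.
- **The rank-sum test in 4.6 should be replaced throughout.** The statement that "two-group comparisons will generally employ Wilcoxon rank-sum tests to protect against violations of normality assumptions" is general and not tied to the screen. A blanket change would alter comparisons that have nothing to do with marker selection.

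**Conclusion.** The point holds in a limited form. The protocol fixes the screening rule, its threshold and its place before adjustment, so this is not detail left for an analysis plan. An analysis plan that followed the protocol would carry the same weakness.

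The markers at risk are novel ones without literature support whose association with gestational age opposes their own effect. For an adjusted OR of 1.25, the chance of passing the screen falls from 91–94% with gestational-age stratum included to about 83% under weak confounding and about 33% under stronger confounding. These figures rest on assumed correlations and gestational-age odds ratios. They show how large the loss can be and do not predict it for any named marker.

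**What to change.** In 4.6.1, screen each candidate in a regression model that contains gestational-age stratum. Keep the p ≤ 0.20 threshold and the literature route as they are. The general test choices in 4.6 and the power statement in 4.4.1 need no change on this account.

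The cost is a change of wording and no new data. Five strata use four degrees of freedom per screen, which is small against 675 infants and still modest for markers measured in a subset, such as the 253 phase-angle evaluations planned in 4.8.1. Markers whose confounding runs in the same direction as their effect pass somewhat less often (about 90% instead of over 99% at r = −0.3 and gestational-age OR 0.67), because they no longer gain from gestational age.

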4.6.2. Multivariable Models

Multivariate models will be used to both simultaneously assess the contributions of the many biomarker predictors as well as to control for factors such as gender, race, products of multiple gestation, birth weight, gestational age at birth, site differences and between hospital variation, in the evaluation of potentially complex associations. Models specified in the protocol will include linear regression for continuous outcomes and logistic regression for binary or ordinal responses. We will provide in the analyses, in addition to tests of significance, confidence intervals for parameters of risk factors and biomarkers, and various approaches to assess the robustness of the estimates to nuisance factors. Particular attention will be paid to unusual observations (outliers) that may have undue influence on the analytical results. Standard regression diagnostics, including residual plots, and influence statistics will be used to identify such observations and examine their effect on analyses.

4.6.3. **Repeated Measurements**

For repeated measures, we will use generalized linear mixed models (GLMM¹⁰⁷) to account for dependence of the measures within subjects. We will first check for patterns in the residuals from the model without any random effect to determine plausible covariance structures that may account for the temporal correlation within subject¹⁰⁸ and then select the best one using routine likelihood-based criteria: maximized likelihood, largest Akaike information criteria (AIC¹⁰⁹), Schwarz information criterion (SBC¹¹⁰). We will use maximum likelihood method (ML) and residual maximum likelihood method (REML) for parameter estimates and significance testing.

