4.6.4. Multiple Comparisons

The analysis approaches described will likely involve a great number of individual statistical tests at both the univariate and multivariate levels. In some cases we utilize global statistical testing (e.g. omnibus contingency table assessments prior to marginal assessments). In other cases it will be appropriate to provide some protection against detecting false positive results by using a stepwise modeling procedure which enters and removes covariates based on

threshold values of p<0.15 and p<0.10 (or otherwise specified in the protocol), respectively, to initially reduce the number of candidate factors.¹¹¹ We are choosing to generally avoid severe adjustments of significance levels using multiple comparison techniques, which would lessen the chance of detecting potentially important biomarkers and other risk factors for severity of respiratory disease.¹¹² We take these more liberal approaches to dealing with multiple comparisons because PROP, an observational study, is considered a hypothesis generating rather than hypothesis testing study. Thus we will generally report significance values related to odds ratios for biomarker prediction of one year outcome as indicators for risk factors that are candidates for confirmation in future studies.

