4.7. Specific Analytic Approaches

The specific analytic approaches to the assessment of which biomarkers play an important role in the prediction of one-year outcome will be discussed. The following sections provide a brief overview of some of the statistical methodologies and considerations that will be used at the time of analysis, both for descriptive purposes, and univariate and multivariate analyses relating biomarkers to one-year outcome(s). For a large study with many exposures or predictors, several outcome variables, and many scientific questions of interest, some of which will evolve with analysis itself, it is not possible to detail analyses of each question. Nonetheless, the types of analyses described here are likely to be used to answer many of the questions that arise. We consider here the principal methodological issues and approaches for dealing with those issues.

4.7.1. **Prediction of Outcome**

The primary focus of PROP is on the delineation of early biomarkers during the NICU hospitalization period that predict *respiratory morbidity through 1 year of age*. We have chosen to approach the assessment of this hypothesis using mixed effect logistic regression, Preliminary analyses will provide a parsimonious set of predictors to be considered in multivariate analyses. A full model will include all main effects (fixed) of parsimonious predictors and a random effect reflecting ICN variation and we will use variable selection techniques such as AIC, BIC and LASSO to select a subset of predictors as a candidate prediction model. All higher-order and interaction terms will be considered as well if there is any indication of effect modifier or non additive effects. For repeated measures, we will use generalized estimating equations (GEE¹¹³) for prediction of the outcome that can be implemented in SAS GENMOD procedure.

Center and Site Variability

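### Biomarkers are selected and then given odds ratios and confidence intervals on the same infants with no allowance for the selection, so retained null markers are under-covered and small true effects are exaggerated.

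*Protocol*

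**What the plan says.** The selection sequence is spread over three sections of the protocol.

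- Section 4.6.1: "factors will be moved forward for further evaluation if either their predictive value produces a p value of" 20% or less, "or they are biomarkers supported in the literature".
- Section 4.6.4: in some cases a stepwise procedure follows, with "threshold values of p<0.15 and p<0.10 (or otherwise specified in the protocol), respectively, to initially reduce the number of candidate factors".
- Section 4.7.1: "we will use variable selection techniques such as AIC, BIC and LASSO to select a subset of predictors as a candidate prediction model".

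None of these steps is assigned separate data, and section 4.9 decides against a hold-out sample.

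For reporting, section 4.6.2 promises "confidence intervals for parameters of risk factors and biomarkers" in addition to significance tests. Section 4.6.4 says "we will generally report significance values related to odds ratios for biomarker prediction of one year outcome", as pointers to markers for later confirmation. Section 4.6 sets a "two-sided significance level (Type I error) of α = 0.05" for most tests, which implies 95% intervals, although no confidence level is stated.

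Section 4.9 concedes that a model looks better in the data used to build it than in independent data. It applies 10-fold cross-validation to the predictive accuracy of the candidate final model, after the model has been derived. The protocol mentions no adjustment of a biomarker's interval or odds ratio for the selection.

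**The concern.** An ordinary Wald interval assumes that the marker would have been reported whatever its estimate. Under the plan's selection rules, a marker not protected by literature support stays only if its estimate is far enough from zero. Conditional on staying, the estimate of a weak effect is on average too large, and the interval of a null marker excludes OR 1 much more often than 5% of the time.

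Section 4.6.4 presents stepwise selection as some protection against false positives. For the intervals and odds ratios of the markers that remain, it works the other way. The stated product of the analysis is a set of candidates for confirmation. A later study sized on an exaggerated odds ratio would be too small, and a reader would take the printed interval as a fair range for the effect.

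**Working it through.** **Inputs from the protocol.** Sample size 750 with 10% missing, so 675 analysed; PRD rate 40%; OR per SD from 1.2 to 1.6 (section 4.4.1); two-sided α = 0.05 (section 4.6); cut-offs from sections 4.6.1, 4.6.4 and 4.7.1. **Not given:** the number of candidates (section 4.1 says only that they are myriad), how many are real, and their correlation. These are assumed below.

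**Step 1: reproduce the plan's own figure.** Power = Φ(√(n·p·(1−p))·ln OR − 1.96). √(675 × 0.40 × 0.60) = √162 = 12.73, and 12.73 × ln 1.25 = 2.84. Φ(2.84 − 1.96) = 81.1%, against the stated figure of above 80%. The subgroup figure in section 4.4.2 also reproduces: n = 135 and OR 1.64 give 80.4%, stated as 80%.

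**Step 2: one null marker under one cut-off.** If the marker is kept when |Z| > c, with two-sided probability s under the null, the 95% interval covers OR 1 with probability 1 − 0.05/s while c < 1.96, and never once c exceeds 1.96.

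- p ≤ 0.20: 1 − 0.05/0.20 = 75%.
- AIC-equivalent (c = √2 = 1.41, s = 0.157): 68%.
- p < 0.10: 1 − 0.05/0.10 = 50%.
- BIC-equivalent (c = √(ln 675) = 2.55, above 1.96): 0%.

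**Step 3: one truly associated marker under one cut-off.** With μ = 12.73 × ln OR, coverage is P(|Z − μ| < 1.96 given |Z| > c). The inflation of the log OR is E(Z given |Z| > c)/μ. The sample-size ratio for a later study sized on the reported OR is 1/inflation².

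| True OR | Cut-off | Coverage | Inflation of log OR | Reported OR | Sample-size ratio |
|---|---|---|---|---|---|
| 1.20 | p ≤ 0.20 | 97.0% | 1.12 | 1.23 | 0.80 |
| 1.20 | p < 0.10 | 96.7% | 1.18 | 1.24 | 0.72 |
| 1.20 | BIC | 93.9% | 1.41 | 1.29 | 0.50 |
| 1.25 | p < 0.10 | 97.2% | 1.08 | 1.27 | 0.86 |
| 1.25 | BIC | 95.9% | 1.22 | 1.31 | 0.67 |
| 1.40 | p < 0.10 | 95.4% | 1.00 | 1.40 | 1.00 |
| 1.60 | p < 0.10 | 95.0% | 1.00 | 1.60 | 1.00 |

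Example, OR 1.20 at p < 0.10: μ = 12.73 × 0.1823 = 2.32; exp(1.18 × 0.1823) = 1.24; 1/1.18² = 0.72.

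**Step 4: several markers together.** Logistic data were simulated with 675 infants and a 40% rate, a p ≤ 0.20 screen, elimination at p < 0.10, and Wald intervals. With 15 to 40 independent candidates, 5 or 6 of them real at OR 1.15 to 1.25, coverage over all retained markers is about 68-87%. In those mixes retained nulls are covered about 45-52% of the time and real markers 94-97%. Other mixes without a BIC cut:

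| Independent candidates | Real | Coverage over retained markers |
|---|---|---|
| 20 | none | 46% |
| 50 | 5 at OR 1.25 | 70% |
| 30 | 5 at OR 1.25 | 78% |
| 20 | 5 at OR 1.25 | 84% |
| 20 | 10 at OR 1.25 | 89% |
| 20 | 20 at OR 1.25 | 97% |

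Without selection, the full model gave 93-96%. With a BIC cut and markers correlated at 0.3 (30 candidates, 5 real at OR 1.25), real markers themselves fell to 82%.

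**Limits.** Stepwise selection was approximated by backward elimination. LASSO, the nursery random effect and the literature route past the screen were not simulated. With 100 to 150 runs per scenario, the Monte Carlo error is roughly 1 to 3 points in most scenarios.

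**The case against.** The strongest reply is that the coverage shortfall is mostly the false-positive question in another form. A null marker whose interval excludes 1 is a test with p < 0.05, and section 4.6.4 openly accepts that risk because the study is hypothesis generating. This largely stands: for independent markers, the loss in the pooled figure comes from retained nulls. But accepting more false positives does not make an interval or an effect size accurate, and the inflation affects true markers too.

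A second reply is that interval methods after model building usually belong in the statistical analysis plan, which is not shown. The sentence in section 4.6.2 is also general and does not restrict intervals to selected markers. That is fair, and it keeps the point modest. Still, the protocol itself fixes the selection rules, promises the intervals and states their use.

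Three stronger readings are tempting, and the documents do not support them.

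- A reader might infer one fixed coverage, such as 75-83%. The protocol gives neither the number of candidates nor the share that is real, so no single figure follows.
- A reader might infer that ordinary intervals are planned for LASSO coefficients. No section says so.
- A reader might infer that confirmation studies would enrol only about 45% of the infants needed. That rests on a true OR of 1.15, below the 1.2 to 1.6 considered in section 4.4.1.

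**Conclusion.** The point holds as a limited one. Selection and reporting use the same infants, and nothing in the protocol adjusts a marker's interval or odds ratio for that; cross-validation of accuracy does not do so.

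Within the protocol's own effect range, coverage for a truly associated marker is close to nominal in the single-marker calculation, and the harm is inflation at the low end: a study sized on the reported value would have about 72% of the infants needed at OR 1.20 after p < 0.10, and about 50% after a BIC-equivalent cut. From OR 1.4, inflation after p < 0.10 is negligible. The pooled coverage figures rest on the assumed candidate mix and should be quoted only with it. The hypothesis-generating label lowers the consequence but does not remove it. This is a cheap improvement, not a flaw that invalidates the study.

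**What to change.** For every candidate biomarker, selected or not, report the OR and 95% CI from one fixed model with the covariates already named in section 4.6.2. These results do not depend on which markers survive selection, and they are the ones on which a later study should be planned.

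For the selected multivariable model, take shrunken odds ratios and intervals from a bootstrap that repeats the whole sequence (screen, any stepwise step, and AIC, BIC or LASSO) in each resample. Label any ordinary post-selection interval as descriptive.

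The cost is a few sentences in the analysis plan, computing time and a longer table. Reported intervals will be wider and reported effects smaller. No additional infants or data are needed.
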